4.5 Randomization Methods

4.5.1 Allocation sequence generation

[figure not shown]
A computer process will be used to generate allocation sequences in a 1:1. Any evidence suggesting increased harm in patients presenting with a contemplated biomarker will lead to the termination of recruitment of patients presenting with this biomarker and will qualify the corresponding biomarker for identifying patients who should not be treated by hydrocortisone plus fludrocortisone (see section 9). A randomization list will be generated beforehand by a computer program and verified according to the procedures of the sponsor, independently from the physicians who will recruit patients.

4.5.2 Stratification:

Randomization will be stratified on the following biomarkers:

- 1. CIRCI
- 2. Endocan
- 3. GILZ
- 4. CPD
- 5. Transcriptomic SRS2
- 6. Endotype B
- 7. COVID-19
- 8. Influenza
- 9. Other respiratory viruses

The full statistical analysis plan will be published before the first interim analyse.

According to the adaptive design of the umbrella trial, the number of biomarker strata is not fixed and will vary with 1) information gained from actual study participants on added-value of a specific biomarker, 2) from new biomarker released by RECORDS WP3-6, 3° from new relevant biomarker released in the literature that will be screened n a trimester basis throughout the study period. These novel biomarkers may include new clinical algorithm or phenotypes, new omic-derived signature, new biological biomarker issued from blood, urine or exhaled air.

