9 STATISTICAL ANALYSIS

9.1 SAMPLE SIZE DETERMINATION

We will enroll a total of at most 1800 patients. Sites are expected to enroll at least 1 or 2 patients per month.

Adaptive outcomes

The goal is to develop an adaptive clinical trial design which evaluates the therapeutic intervention of targeted therapy, identifies subset of subjects who respond better to the experimental therapy.

Sequential analyses will use the number of vasopressor-free days at day 28 as the measure of efficacy, and the occurrence of severe adverse events within the first 28 days as the measure of toxicity. According to the literature (the APPROCCHS trial), the number of vasopressor-free days at day 28 in the hydrocortisone+fludrocortisone group was 17.1 ± 10.8 versus 15.0 ± 11.1 in the placebo group. Thus, a sample of 176x2=352 patients achieves 80.04 % power to reject the null hypothesis of equal means when the mean difference between arms is 3 days with SD of 10 days, and with a significant level (alpha) of 0.05 using a two-sample t-test. For interactions to be detected with the same power as the overall effect, sample sizes should be inflated (Brookes 2004); estimated here at a multiple of fourfold; therefore, to handle potential dropouts, a sample of 1800 patients was considered to be enrolled.

Note that Bayesian inference will be used for sequential analyses, so that no inflation of type I error rate is to be corrected.

Primary outcome

To detect a 10% absolute risk reduction (from 45% to 35%) in the day 90 mortality, a sample size of 373 evaluable patients per arm (thus a total of 746 patients) is required to reach a 80% power. The planned sample of 1800 patients will achieve a 99.16%

power to reject the null hypothesis of equal mortality when the difference between arms is 10% overall, and with a 5% alpha level.

Sample sizes were computed using PASS 15 software (2017).

The power to detect this difference within each group of analysis will depend on the prevalence of each biomarker of interest.

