9.2 STATISTICAL METHODS

9.2.1 Adaptive Bayesian analyses

Clinical trial methodology needs to adapt to personalized medicine by including more frequent interim analyses of accumulating data, or by making greater use of those biomarkers information (Saad 2017; Janiaud 2019). An adaptive design is a clinical trial design that allows adaptations or modifications to aspects of the trial after its initiation without undermining the validity of the trial.

Therefore, the aim of the sequential analyses will be to detect treatment-by-biomarker interactions, that is, whether the treatment effect may be different according to biomarkers, that may potentially stop the recruitment of patients presenting with certain levels of that biomarker if there is any evidence that it interacts negatively with the outcome. Treatment effect will be assessed on two main outcome measures, namely a tolerance measure (to detect potential deleterious effects of treatment in some subsets) and an early surrogate efficacy measure (to detect a potential futility to continue treatment evaluation in some cohorts). As described above (section 4.8.2), the tolerance measure will be the occurrence within the first RECORDS" protocol, version 4.0 of 03/03/2021

7, 14 and 28 days of any grade 3 or over adverse events such as hospital-acquired infections, hyperglycemia, hypernatremia, neurological disorders, and the efficacy measure will be the number of vasopressor-free days within the first 28 days.

Search for treatment-by-cohort interactions will be based on each endpoint, and each cohort, separately. Let A and B denote the 2 treatment arms. The treatment effect, 0, of A over B will be considered as the parameter of interest.

Let consider a set of K biomarkers available at baseline, with $x_i = (x_{1i}, \dots, x_{Ki})$ the set of biomarkers for subject *i*, and $Y_{ii} = 1$ the outcome of subject i in arm j.

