We will use a Bayesian inference. This is in line with the growing literature to propose Bayesian approaches in randomized clinical trial (), including to identify subpopulations with enhanced treatment effects (Simon 2018). Moreover, it allows to go further than the "statistically significant" findings based on p-values (Wasserstein 2019; Amrhein 2019). Last, Unlike in the frequentist evaluation of the influence condition, the Bayesian evaluation of the influence condition has the advantage of separating the parameters of clinical relevance and risk tolerance (Millen 2014), as detailed below.

Search for treatment-by-cohort interactions will be based on each biomarker and outcome, separately. Treatment-by-covariate interaction will be measured by a Bayesian criterion proposed by Millen (2014), based on the posterior probability of the 'interaction condition' defined in terms of the subpopulation effect sizes estimates:

$P(\hat{\theta}_+/\hat{\theta}_- \geq \lambda_1 | X) \geq \gamma_1,$

where X is the observed data, $\hat{\theta}_+$ is the treatment effect on the efficacy outcome in one subset and $\hat{\theta}_-$ in the remaining subpopulation, λ_1 is a threshold of clinically meaningful effect, close to that proposed by Morita (2014), and γ_1 represents the information threshold for decision-making. Inversely, it will apply to the tolerance outcome, based on

 $P(\hat{t}_+/\hat{t}_- \ge \lambda_2 | X) \ge \gamma_2$, where \hat{t}_+ is the treatment effect on adverse event in one subset and \hat{t}_- in the remaining subpopulation, λ_2 is a threshold of clinically deleterious effect, and γ_2 represents the information threshold for decisionmaking.

The estimates $\hat{\theta}_i$ or $\hat{\tau}_i$ will be defined according to the type of the endpoint, either continuous, with $\hat{\theta}_j$ = $\frac{\hat{\mu}_{Aj} - \hat{\mu}_{Bj}}{\hat{\sigma}_{i}}$, is the effect size defined within each subgroup as the mean treatment

difference divided by the common standard deviation, or binary $\hat{\tau}_j = \frac{\hat{p}_{Aj} - \hat{p}_{Bj}}{|\bar{p}_j(1 - \bar{p}_j)|}$ where \bar{p}_j is the estimated

average adverse event rate.

Noninformative prior distribution will be considered.

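### Section 9.1 wrongly says that Bayesian sequential analyses need no type I error correction; false cohort closures can become likely unless the decision thresholds are calibrated

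*Protocol*

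**What the plan says.** Under the adaptive outcomes in Section 9.1, the protocol sizes the monitoring endpoint (vasopressor-free days at day 28) with a two-sample t-test at alpha 0.05, then adds that "Bayesian inference will be used for sequential analyses, so that no inflation of type I error rate is to be corrected".

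Section 9.2.1 describes the monitoring. A signal is declared when the posterior probability that the ratio of treatment effects (one subset over the remainder) is at least lambda reaches gamma, with one pair of thresholds for efficacy and one for tolerance. On the prior: "Noninformative prior distribution will be considered". On the tests: "Search for treatment-by-cohort interactions will be based on each endpoint, and each cohort, separately". On the endpoints: "Treatment effect will be assessed on two main outcome measures, namely a tolerance measure", the other being early efficacy. Tolerance is read within "7, 14 and 28 days of any grade 3 or over adverse events".

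Section 4.5.2 lists nine biomarkers and adds that "the number of biomarker strata is not fixed and will vary with" incoming information. Section 4.5.1 gives the consequence: "Any evidence suggesting increased harm in patients presenting with a contemplated biomarker will lead to the termination of recruitment", and the biomarker then qualifies as identifying patients who should not receive the study drugs. Section 9.2.1 is softer and says that recruitment may potentially stop.

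**The concern.** Being Bayesian does not by itself protect a decision rule against false signals. Protection would have to come from an informative or sceptical prior, from shrinkage across cohorts, or from thresholds chosen with the number of looks and tests in mind. The protocol states a noninformative prior and separate searches, and tells the reader that nothing needs correcting. Each extra look gives chance another opportunity to cross the threshold, and so does each extra biomarker or endpoint.

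A false signal would be costly. It can close a cohort that responds like everyone else, and it can become a claim that a biomarker marks patients who should not be treated. Whether biomarkers modify the response to treatment is the question the trial exists to answer.

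**Working it through.** **The protocol's own figures.** It states no false-closure rate, so only its power figures can be reproduced.
- Monitoring endpoint: 176 per arm, difference 3 days, SD 10. Noncentrality = 3 / (10 × √(2/176)) = 2.81; two-sided t-test power 80.1% (stated 80.04%).
- Primary outcome: 45% versus 35%. The unpooled formula gives 373 per arm (stated 373). With 900 per arm, power is 99.14% (stated 99.16%).

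That arithmetic is not at fault. It describes a single look at one overall comparison.

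**Why the sentence fails in general.** In the simplest case, a flat prior and the rule P(difference > 0 | data) ≥ gamma, the rule is the same as Z ≥ z(gamma). At gamma 0.95 a single test gives a false signal 5.0% of the time with one look, 13.0% with five equally spaced looks and 17.3% with ten (200,000 simulated paths). This shows the mechanism; it is not the protocol's rule.

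**The protocol's rule.** P(θ₊/θ₋ ≥ λ | X) ≥ γ, with θ the standardised treatment difference in the subset (θ₊) and in the remainder (θ₋).

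Inputs from the protocol: at most 1800 patients, 1:1 allocation, noninformative prior, 9 biomarkers × 2 endpoints = 18 tests.

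Assumptions: prevalence 0.3 for each biomarker, independent biomarkers, two independent normally distributed endpoints, five looks, and the same true effect in every subset, so that every signal is false.

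Effect sizes: Section 9.1 cites 17.1 versus 15.0 days with SDs 10.8 and 11.1. Then 2.1 / √((10.8² + 11.1²)/2) = 2.1 / 10.95 = 0.19, taken as 0.2. The planning effect is 3/10 = 0.3, so 0.2 and 0.4 bracket it.

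Precision explains the result. With n patients split 1:1, the standard error of θ is 2/√n. If the five looks are equally spaced, the first has 360 patients: 108 in the subset (standard error 0.19) and 252 outside it (0.13). A common effect of 0.2 is then about as large as the noise.

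**False signals per test and over 18 tests, gamma 0.95**, using 1 − (1 − p)¹⁸:

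| Effect, lambda | p, one look | p, five looks | Any of 18, one look | Any of 18, five looks |
|---|---|---|---|---|
| 0.2, 1 | 3.0% | 5.0% | 42% | 60% |
| 0.4, 1 | 4.8% | 11.8% | 59% | 90% |
| 0.4, 1.25 | 0.6% | 2.7% | 10% | 39% |

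Other simulations of the first row at five looks gave 52%, 57% and 70%; the last rose from about 53% at one look. The set-up that gave 57% at five looks gave 72% at ten. Hence the range of about 50–70%.

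**Dependence on the thresholds**, effect 0.2, five looks, any of 18 tests (250 runs):

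| | gamma 0.90 | 0.95 | 0.975 | 0.99 |
|---|---|---|---|---|
| lambda 1 | 89% | 57% | 30% | 4% |
| lambda 1.25 | 57% | 22% | 6% | 0.4% |
| lambda 1.5 | 28% | 4% | 0% | 0% |

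For lambda 1.5 and gamma 0.95, the simulations gave about 2–4%.

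**No effect anywhere.** The ratio is then too unstable to reach a high posterior probability. The simulations gave at most 3% over 18 tests, and mostly none.

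**The case against.** A Bayesian would answer that a posterior probability keeps its meaning whatever the stopping rule, so type I error is the wrong yardstick. That is fair for a prior that expresses real belief. It is weak for a noninformative prior applied to 18 separate searches, and Section 9.1 itself uses a frequentist alpha in the same paragraphs.

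The stronger objection concerns size. A reader might infer that the posterior threshold behaves exactly like an uncorrected one-sided Z-test, so that false closures are likely whatever the thresholds. The documents do not support this. The rule is a ratio with a clinical margin lambda; it almost never fires when there is no effect at all, and strict pairs of lambda and gamma keep the risk low even with a common effect. The numerical thresholds and the number of looks may be in the statistical analysis plan, which Section 4.5.2 promises before the first interim analysis. Their absence from the protocol is not a fault.

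Three further inferences also go too far:
- That the plan forbids calibration. It says only that no inflation is to be corrected; gamma could still be chosen by simulation.
- That recruitment stops on literally any evidence. The sentence in 4.5.1 refers to Section 9, where the lambda and gamma rule stands and the wording is that recruitment may stop.
- That 9.1 sets a 5% test within each cohort, calling for a family-wise procedure. Its 5% attaches to the overall comparison; for the groups it says only that power depends on prevalence.

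The count of 18 independent tests is also a simplification. One patient may carry several biomarkers, the three tolerance windows are nested (9.1 names only 28 days), and the list of nine can grow or shrink. Overlap lowers the totals; added cohorts or time points raise them.

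**Conclusion.** The sentence in Section 9.1 is wrong as a justification and should not stand. The consequence is conditional: false cohort closures can become likely unless the thresholds are calibrated. Under the stated assumptions, at gamma 0.95 and five looks, the overall chance of a false signal runs from near zero (no effect anywhere, or a wide margin lambda) to about 90% (effect 0.4, lambda 1). The demanding case is a treatment that works equally well in all patients, since the ratio rule hardly fires without any effect. These figures count each signal as a closure and treat the 18 tests as independent. That spread makes calibration decisive for whether the monitoring rule is sound. Confidence is high that the sentence is wrong; the size in this trial cannot be fixed from the protocol alone.

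**What to change.** Delete the sentence. State instead that lambda and gamma for both endpoints are set by simulating the whole design: the number and timing of looks, the cohorts and their overlap, both endpoints including the tolerance windows, the possible addition of cohorts, and scenarios with a common non-zero effect as well as no effect. The thresholds should hold the chance of any false cohort closure at or below a level that the protocol names. Report these operating characteristics, per cohort and overall, before the first interim analysis; the statistical analysis plan already due by then is the natural place.

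The cost is simulation work and some wording. Stricter thresholds may mean that a true signal is acted on somewhat later, and the same simulations should show by how much. Eligibility, treatment and the maximum sample size need not change.

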15.4.5 Annex 5 : Ventilator procedures	
LIST OF ABBREVIATIONS	

Abbreviation	Explanation				
ADR	Adverse Drug Reaction				
AE	Adverse Event				
AGEPS	Agence générale des équipements et produits de santé-APHP				
ANSM	gence nationale de sécurité du médicament et des produits de santé				
APHP	Paris Public Hospital Assistance				
CMU	Couverture Maladie Universelle				
CRF	Case Report Form				
CRP	C-reactive protein				
CTA	Clinical Trial Application				
DSMC	Data Safety Monitoring Committee				
DRCI	Delegation of Clinical Research and Innovation				
eCRF	Electronic Case Report Form				
EDC	Electronic Data Capture				
ELISA	Enzyme Linked ImmunoSorbent Assay				
FiO2	Fraction of inspired oxygen				
HRQoL	Health Related Quality of Life				
ICU	Intensive Care Unit				
IPDMA	Individual Patient Data Meta-Analysis				
IRB	Institutional Review Board				
PaO2	Partial pressure of arterial oxygen				
PaCO2	Partial pressure of arterial carbon dioxide				
RCT	Randomized Controlled Trial				
REB	Research Ethics Board				
SADR	Serious Adverse Drug Reaction				
SAE	Serious Adverse Event				
SOFA score	Sequential Organ Failure Assessment score				
SUADR	Serious Unexpected Adverse Drug Reaction				
SUSAR	Suspected Unexpected Serious Adverse Reaction				
URC HUPIFO	Paris Ile de France Ouest Clinical Research Unit				
WHO	World Health Organization				

STUDY SUMMARY

Title	Rapid rEcognition of COrticosteroid Resistant or sensitive Sepsis -						
Acronym/reference	RECORDS						
Coordinating	Pr [name]						
investigator and							
Scientific Director							
Sponsor	Assistance Publique – Hôpitaux de Paris						
Clinical Sites	French adult general ICUs						
Background	WHO estimates that, yearly, 30 million people develop sepsis and						
	11million die. APROCCHS, a phase 3, placebo-controlled trial, demonstrated a 6% absolute reduction in sepsis mortality with hydrocortisone+fludrocortisone. A number of factors may positively/negatively impact corticosteroids (CS) benefits in sepsis						

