	e. Transcriptomic SRS2
	f. Endotype B
	g. PCR COVID-19
	h. PCR Influenza
	i. PCR other respiratory virus
	6. Affiliation to a social security system or to an universal health
	coverage (Couverture Maladie Universelle, CMU).
	7. Patients under guardianship or curatorship will be included.
	8. Patients in case of simple emergency (legal definition) will be
	included.
	9. Patients managed with covid 19 and having biological
	samples available
Exclusion Criteria	1. Pregnancy;
observational	2. Expected death or withdrawal of life-sustaining treatments within 48 hours;
phase: (N°1,2,3)	3. Previously enrolled in this study
interventional	4. Formal indication for corticosteroids according to most recent
phase:	international guidelines
(N°:1,2,3,4,5,6,7,8).	5. Vaccination with live virus within past 6 months
(11,1,2,0,4,0,0,7,0).	6. Hypersensitivity to hydrocortisone or fludrocortisone or any of their
	excipients (spc)
	7. Women of childbearing potential not using contraception
	8. Nursing women
Study Intervention	-Observational phase (run-in period): additional biological samples
	For the restrospective part (Covid patients): telephone
	follow-up -Interventional phase:
	Investigational products or their placebo will be administered to
	patients on the basis of RECORDS signatures
	Investigational products included:
	- Hydrocortisone hemisuccinate 50 mg: one intravenous injection
	every 6 hours, and
	- 9 alpha fludrocortisone 50 µg: one tablet per day via a nasogastric
	tube.
	All treatments will be stopped after 7 days or until the patient has left the intensive care unit (whichever occurs first) without tapering off.
Randomization	Web-based randomization system available 24/7. Eligible patients will
(Interventional	be randomized in a 1:1 ratio to corticoseroids or matching placebo.
phase)	We will use permuted blocks of undisclosed and variable size and
	stratify randomization by site and biomarkers.
Sample Size	We will enroll a total of at most 1800 patients in this adaptative trial.
	Sites are expected to enroll at least 1 or 2 patients per month. By
	enrolling 376 evaluable patients per arm, the study will have 80%
	power to detect a 10% absolute risk reduction (from 45% to 35%, which
Study duration	corresponds to a 20% relative risk reduction). Inclusion period: 48 months:
Study duration	Treatment 7 days and follow-up: 6 months.Daily during ICU stay and
	telephone follow-up at 6 months.
	Total study period: 54 months
L	

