1.4.2 The challenge of corticosteroids responsiveness in sepsis

The crude absolute reduction in mortality in these two trials was about 6.5%. It is likely that among the heterogeneous population of sepsis, some patients may draw much substantial survival benefit whereas others may be harmed. Corticosteroids survival benefit is not affected by age, gender, disease severity, type of infection, source of infection, or type of pathogens (Lamontagne 2018). There is currently no diagnostic test for CS sensitivity/resistance in sepsis. The scientific community is competing to identify markers delineating between patients who draw survival benefit from corticosteroids (CS-sensitive sepsis) and those who may be harmed (CS-resistant sepsis). In sepsis, the deregulated response may result in systemic inflammation and organs damage, or immune paresis and secondary infections (van der Poll 2017). Obviously, patients with systemic inflammation may benefit from CS whereas those with immune paresis may deteriorate. We looked for an interaction between survival in response to corticosteroids and the presence of CIRCI according to the ACTH test results (cortisol increment of less than 9 μ g/dL). The benefits from corticosteroids were more important in patients with CIRCI in the Ger-Inf-05 trial but not in

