2.1 PRIMARY OBJECTIVES OF EACH ANALYSIS BY BIOLOGICAL MARKER

To compare the effect hydrocortisone plus fludrocortisone vs. placebo on a composite of death or persistent organ dysfunction – defined as continued dependency on mechanical ventilation, new renal replacement therapy, or vasopressors – assessed at 90 days on intensive care unit (ICU) adults and having different biological profiles for immune responses and corticosteroids bioactivity.

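### The primary-outcome sample size in section 9.1 is worked for day-90 mortality instead of the composite, disagrees with the Study Summary, and its 99.16% power is not the power of the per-biomarker primary objective

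*Protocol*

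**What the plan says.** Section 2.1 of the Protocol is headed "PRIMARY OBJECTIVES OF EACH ANALYSIS BY BIOLOGICAL MARKER" and compares active treatment with placebo "on a composite of death or persistent organ dysfunction" at 90 days. Section 5.14.1 makes the primary endpoint a binary composite in which death is one way of failing. The Study Summary also gives a composite.

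The primary-outcome part of section 9.1 plans for a 10-point absolute reduction, "from 45% to 35%) in the day 90 mortality, a sample size of 373 evaluable patients per arm", for 80% power. It continues: "The planned sample of 1800 patients will achieve a 99.16" per cent power, against a null hypothesis of equal mortality, for a 10-point difference described as overall, at a 5% alpha level. Its last sentence says that power within each group of analysis will depend on biomarker prevalence. It gives no prevalence and no power figure at that level.

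The Study Summary, for 45% to 35% with no outcome named, gives "376 evaluable patients per arm, the study will have 80" per cent power and says that this "corresponds to a 20% relative risk reduction".

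Section 5.11.4 says that COVID-19 patients receive only fludrocortisone or its placebo as study drug. The other cohorts compare hydrocortisone plus fludrocortisone with placebos.

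**The concern.** There are three separate matters.

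1. **Endpoint.** Death is one component of the composite, so the composite rate cannot be lower than the mortality rate. Either 45% is mortality and the primary endpoint has no planning rate, or 45% is the composite and section 9.1 mislabels it. The text does not settle which.

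2. **Figures.** Two sizes are quoted for the same inputs with no test named, and the relative reduction does not follow from the two rates beside it.

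3. **Level.** The only power figures given for the primary outcome, 80% at 373 or 376 per arm and 99.16% at 1800, are for one two-arm comparison. The primary objective is one comparison per biomarker cohort. Someone reading a cohort result against the 99% would be using a power that does not belong to it. The overall comparison also mixes two contrasts, because the COVID-19 cohort tests fludrocortisone alone.

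**Working it through.** **Inputs.** From section 9.1: p1 = 0.45, p2 = 0.35, 80% power, 5% alpha, maximum 1800 patients. From section 4.5.1: 1:1 allocation, so 900 per arm. Sidedness is not stated; two-sided reproduces the figures. Hence z(0.975) = 1.960, z(0.80) = 0.842, and (1.960 + 0.842)² = 7.849.

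**Reproducing the two sizes.**
- The variance sum is 0.45 × 0.55 + 0.35 × 0.65 = 0.475.
- Unpooled z-test: n = 7.849 × 0.475 / 0.10² = 372.8, so 373 per arm (section 9.1).
- Pooled z-test, mean rate 0.40: n = [1.960 × √(2 × 0.40 × 0.60) + 0.842 × √0.475]² / 0.10² = 375.6, so 376 per arm (Study Summary).
- The gap is 3 per arm, or 0.8%.

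**Reproducing the 99.16%.** At 900 per arm, the standard error is √(0.475/900) = 0.02297. Then 0.10/0.02297 − 1.960 = 2.393, and Φ(2.393) = 99.16% (unpooled). The pooled version gives 99.14%.

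**Relative reduction.** 0.10/0.45 = 22.2%. A 20% relative reduction from 45% would end at 36%, which needs 466 per arm (pooled).

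**Composite in place of mortality.** The Protocol gives no control rate labelled as the composite, so the rates below are assumptions, with the 10-point difference kept (pooled test).

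| Assumed control rate | n per arm, 80% power | Power at 900 per arm |
|---|---|---|
| 50% | 388 | 99.0% |
| 55% | 392 | 98.9% |
| 60% | 388 | 99.0% |

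**Power at the level of the primary objective.** Take cohort size as 1800 × prevalence, half per arm, at 45% versus 35% (pooled test): power = Φ{[0.10 − 1.960√(0.48/n)] / √(0.475/n)}, with n per arm. The prevalences are assumptions.

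| Assumed prevalence | Cohort size | Power |
|---|---|---|
| 10% | 180 | 28% |
| 20% | 360 | 49% |
| 30% | 540 | 66% |
| 40% | 720 | 78% |
| 50% | 900 | 87% |

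For 80% power the cohort must hold 746 (unpooled) to 752 (pooled) patients. 746/1800 = 41.4% and 752/1800 = 41.8%, so about 42% prevalence.

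**Where 1800 comes from.** Section 9.1 derives it from vasopressor-free days at day 28: 352 patients for the main effect, times four for interactions (352 × 4 = 1408), raised to 1800 for dropouts. The primary-outcome calculation does not set it.

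**The case against.** The best defence is that little here changes a design number. The endpoint mismatch may be only a slip in labelling, since the Study Summary gives 45% to 35% without naming mortality. Substituting the composite moves the size by a dozen or so patients per arm. The 373 and 376 are both valid, and the 20% feeds no calculation. All of that stands, and it is why the sample size should stay. It does not remove the need to correct statements that disagree with the Protocol's own endpoint and with each other.

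It can also be said that section 9.1 hides nothing: it calls the comparison overall and says that cohort power depends on prevalence. That is fair. The 99.16% is neither miscalculated nor claimed for a cohort. What remains is that the level at which section 2.1 sets the primary objective has no power figure. A full table could be left to the analysis plan, but the Protocol should not leave its only figures to stand for a different comparison.

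Two stronger readings are tempting and should not be drawn.

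- A reader might infer that most cohorts cannot reach 376 per arm. The Protocol gives no cohort prevalences. Section 1.3 mentions poor adrenal activity in almost half of patients, which, if it carried over to the CIRCI cohort, would put that cohort above 42%. Strata may also be stopped or added, so final cohort sizes need not be 1800 × prevalence.
- A reader might infer that 10 points is too optimistic, because the Study Summary says that an earlier trial "demonstrated a 6% absolute reduction in sepsis mortality with hydrocortisone+fludrocortisone" and section 1.4.2 says "The crude absolute reduction in mortality in these two trials was about 6.5" per cent. Those are mortality effects in patients not selected by biomarker. A 10-point target on a composite, in a trial looking for better responders, is a design choice and not an error.

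**Conclusion.** The point holds as a correction of stated design figures. Section 9.1 sizes and powers the primary outcome on an endpoint that is not the primary endpoint. The Protocol gives two sizes for the same inputs, and one relative reduction that should read 22%. The 99.16% is right for a single comparison of all 1800, which includes COVID-19 patients randomised to fludrocortisone alone. It is not the power of the per-biomarker primary objective.

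The endpoint change is numerically small if the 10-point difference is kept and the composite control rate is 50-60%, both assumptions. The larger gap is between overall and cohort power, and its size depends on prevalences that the Protocol does not state and on cohorts filling in proportion to prevalence.

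**What to change.** - Keep the maximum of 1800, which rests on the vasopressor-free-day interaction calculation.
- In section 9.1, name the composite as the endpoint of the primary-outcome calculation and of its null hypothesis, with its own assumed control rate and the reason for it.
- Name one test and its sidedness, and give the same size in section 9.1 and the Study Summary.
- Correct 20% to 22% in the Study Summary.
- Say that the 99% applies to the pooled comparison of all patients, that this includes the fludrocortisone-only COVID-19 cohort, and that it is not the power of the per-biomarker primary objective. Give within-cohort power over a range of assumed prevalences, marked as assumptions.

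The cost is some rewording and one short table. Recruitment and treatment are untouched. The price is that the power shown for the primary objective will look less favourable than 99%.
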